### 5.4. PER PROTOCOL ANALYSIS SET [PPAS]

The per-protocol analysis set (PPAS) will contain all patients in the FAS who did not experience any major protocol deviations which impact the efficacy conclusions of the study. Examples of major protocol deviations which may affect inclusion in the PPAS include:

- Treatment compliance of <80% or ≥120% of the prescribed dosage.
- Clinically significant discrepancies between planned and actual treatment.
- Receipt of prohibited medications.
- Violations of the entry criteria.

### 5.5. SAFETY ANALYSIS SET [SAF]

The safety analysis set (SAF) will contain all patients in the RND set who receive at least one dose of study drug.

If there is any doubt whether a patient was treated or not, they will be assumed treated for the purposes of analysis.

### 5.6. PHARMACOKINETIC ANALYSIS SET [PK]

The pharmacokinetic analysis set (PK) will include all patients in the RND with at least one valid PK measurement.

### 5.7. COMPLETERS ANALYSIS SET [CAS]

The completers analysis set (CAS) will contain all patients in the FAS who completed the full treatment period, as recorded in treatment disposition page of the eCRF.

---

Document:	C:\Users\q718413\Documents\NEP-MDD-201_SAP_v1.0_Final_06Dec2018.docx		
Author:	[name]	Version Number:	1.0
		Version Date:	06Dec2018

Template No: CS\_TP\_BS016 Revision 4  
Effective Date: 01Apr2016

Reference: CS\_WI\_BS005

Copyright © 2009, 2010, 2012, 2016 Quintiles Transnational Corp. All rights reserved.  
The contents of this document are confidential and proprietary to Quintiles Transnational Corp. Unauthorized use, disclosure or reproduction is strictly prohibited.

## 5.8. MADRS NON-RESPONDERS ANALYSIS SET [MNRAS]

The MADRS non-responders analysis set (MNRAS) will contain all patients in the FAS who have a Week 2 investigator-administered MADRS total score that is >50% of the baseline MADRS total score. This determination will be made programmatically using the Baseline and Week 2 MADRS total scores.

## 6. GENERAL CONSIDERATIONS

### 6.1. REFERENCE START DATE AND STUDY DAY

Study Day will be calculated from the reference start date, and will be used to show start/stop day of assessments and events.

Reference start date is defined as the day of the first dose of study medication (Day 1).

- If the date of the event is on or after the reference date then:

Study Day = (date of event – reference start date) + 1.

- If the date of the event is prior to the reference date then:

Study Day = (date of event – reference start date).

In the situation where the event date is partial or missing, the date will appear partial or missing in the listings, and Study Day, and any corresponding durations will be presented based on the imputations specified in [Appendix 2](#); Partial Date Conventions.

### 6.2. BASELINE

Unless otherwise specified, baseline is defined as the last non-missing measurement taken prior to reference start date (including unscheduled assessments). For this study, the reference date will be the date of first study drug dosing. In the case where the last non-missing measurement and the reference start date coincide, collection time, where available, will be compared with first dose time to determine whether the measurement is pre-baseline or post-baseline. If time is not available the measurement will be considered pre-baseline, but Adverse Events (AEs) and medications commencing on the reference start date will be considered post-baseline.

### 6.3. RETESTS, UNSCHEDULED VISITS AND EARLY TERMINATION DATA

In general, for by-visit summaries, data recorded closest to the nominal visit day will be presented. [Section 6.4](#) includes more details regarding visit windowing conventions and data handling for by-visit summaries.

Early termination data will be considered when assigning values to a visit window.

---

Document:	C:\Users\q718413\Documents\NEP-MDD-201_SAP_v1.0_Final_06Dec2018.docx		
Author:	[name]	Version Number:	1.0
		Version Date:	06Dec2018

Template No: CS\_TP\_BS016 Revision 4  
Effective Date: 01Apr2016

Reference: CS\_WI\_BS005

Copyright © 2009, 2010, 2012, 2016 Quintiles Transnational Corp. All rights reserved.  
The contents of this document are confidential and proprietary to Quintiles Transnational Corp. Unauthorized use, disclosure or reproduction is strictly prohibited.

Analysis Plan

Listings will include scheduled, unscheduled, retest and early discontinuation data.

## 6.4. WINDOWING CONVENTIONS

For each visit, a window will be defined such that the lower and upper bounds of each window is generally the midpoint between 2 consecutive study visits.

### Visit Analysis Windows for Efficacy and Safety Variables Evaluated by Visit

	Baseline	Week 1	Week 2	Week 4	Week 6	Week 8
Scheduled Visit Day a	1	8	15	29	43	57
MADRS and other tests scheduled at each visit	≤1	2 – 11	12 – 22	23 – 36	37 – 50	≥51
HAM-A, PK, ECGs, and other tests scheduled at similar visits	≤1			2 – 43		≥44
Pain Questionnaire	≤1		2 – 22	23 – 36	37 – 50	≥51
SHAPS	≤1	2 – 11	12 – 22	23 – 43		≥44
FERT	≤1	2 – 11	12 – 22			
Urine Drug and Alcohol Screen	1	8		29	43	57

a Days are relative to the first dose of study medication.

Note: Any value collected after the administration of first dose on Day 1 will be grouped under Day 2.

Visit windowing will be applied to remap early termination visit data only. Thus, more than one result for a parameter may be obtained in a visit window. In such an event, the result from the scheduled visit will be used over the early termination visit.

The study window convention will not be applied to the eCRF data listings. The data listings for eCRF data will display the raw data as collected and entered in the eCRF.

Windowing will be applied to the data prior to any missing data calculations.

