## 9 STUDY PROCEDURES

A visit window of +/- 1 day is acceptable for all visits with the exception of Visit 2 (randomization) and Visit 8 (safety follow-up). Every effort should be made to have the same qualified rater perform scales at each visit for a given patient. As much as possible, schedule the patient to complete the PRT/EEfRT tasks at approximately the same time at all visits where they are conducted. Only outcome measures or assessment tools provided by the Sponsor for this study are allowed to be used. Study drug is administered in clinic at Visits 2, 3, 4, 5, and 6 and patients should be reminded to withhold home-dosing on these days.

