#### 15.1.4. SENSITIVITY ANALYSIS OF PRIMARY EFFICACY VARIABLE

The following sensitivity analyses will be conducted on the change from baseline in investigator-administered MADRS total score to ensure robustness of the primary efficacy analysis. The FAS will be used for all sensitivity analyses unless otherwise specified.

- The primary efficacy analysis will be repeated on the PPAS, CAS, and MNRAS analysis sets.
- The MMRM model used for the primary efficacy analysis will be used to analyze the change from Baseline in investigator-administered MADRS total score at each post-Baseline visit. For each visit the difference in LS Means between BTRX-246040 and placebo will be presented alongside the 2-sided 95% confidence interval and P-value.
- ANCOVA will be used to analyze the change in investigator-administered MADRS total score from baseline to week 8, with missing data imputed. The ANCOVA model will include treatment group, investigative site as fixed effects and baseline investigator-administered MADRS total score as a covariate. Only the MADRS total score will be imputed where missing, the individual component scores will not be imputed. Imputation will be performed following visit window remapping. The following two methods of data imputation will be used:
  - Multiple imputation using Rubin's rules with SAS Proc MI and MIANALYSIS.
  - Single imputation by last observation carried forward (LOCF).
- Finally, the change from baseline in the computer-administered MADRS total score will be analyzed using the same method as the primary efficacy analysis.

Forest plots of the treatment difference and confidence intervals will be created for the primary analysis and each of the efficacy analyses.

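### SAP window rule removes some early-termination MADRS scores before imputation, so the LOCF sensitivity analysis does not always carry the last observation

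*SAP*

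**What the plan says.** Protocol 13.2.8.2 promises an ANCOVA of the Week 8 change in Investigator-administered MADRS with missing values filled by multiple imputation and, separately, by LOCF. SAP 15.1.4 keeps both, and SAP 3.3 declares no departures from the protocol.

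SAP 6.4 sets the windows. Their "lower and upper bounds of each window is generally the midpoint between 2 consecutive study visits". The rule is limited in scope: "Visit windowing will be applied to remap early termination visit data only". Where a window then holds two results, "In such an event, the result from the scheduled visit will be used over the early termination visit".

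The order of operations is stated twice. SAP 6.4 says: "Windowing will be applied to the data prior to any missing data calculations". SAP 15.1.4 says of the primary endpoint: "Imputation will be performed following visit window remapping". Neither section makes an exception for LOCF.

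**The concern.** Take a patient seen on Day 29 who terminates on Day 35. Both MADRS scores fall in the Week 4 window (Days 23–36). The Day 35 score gives way to the Day 29 score. Imputation then runs on what is left, so LOCF carries Day 29 to Week 8. The last observation was collected but is not the one carried.

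An analysis reported as LOCF would then follow a different rule from the one its name gives, without the SAP declaring a change. The score set aside is the one taken as the patient left. If patients leave because they are getting worse, and more do so in one arm, LOCF would miss some of that worsening in that arm. The protocol also asks sites to make every effort to obtain end-of-treatment assessments from early leavers (8.3.1, 9.7), so it is odd to collect the score and then bypass it in the one analysis built on the last score.

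**Working it through.** **Inputs**

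- Nominal visit days 8, 15, 29, 43 and 57, and the MADRS windows: table in SAP 6.4.
- Visit tolerance: "A visit window of +/- 1 day is acceptable for all visits", apart from Visits 2 and 8 (Protocol 9).
- Dropout timing, ET attendance and the lag from stopping to the ET visit: not in the documents, so assumed below.

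**Step 1: reproduce the windows.** The midpoints are (8+15)/2 = 11.5, (15+29)/2 = 22, (29+43)/2 = 36 and (43+57)/2 = 50. With ties going to the earlier window, these give the MADRS bounds in the table.

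**Step 2: count the days on which an ET score is overridden.** These are the days after the nominal visit but still inside its window.

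| Window | Days | Nominal visit | Override days | Count | Largest age gap |
|---|---|---|---|---|---|
| Week 1 | 2–11 | 8 | 9–11 | 3 | 11 − 8 = 3 |
| Week 2 | 12–22 | 15 | 16–22 | 7 | 22 − 15 = 7 |
| Week 4 | 23–36 | 29 | 30–36 | 7 | 36 − 29 = 7 |
| Week 6 | 37–50 | 43 | 44–50 | 7 | 50 − 43 = 7 |
| Week 8 | 51 onward | 57 | none before Day 57 | 0 | – |

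The total is 3 + 7 + 7 + 7 = 24 days. A scheduled visit held one day early adds one day to the age gap. An ET visit on Days 51–56 becomes the Week 8 value, so nothing is carried for it.

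**Step 3: share of possible ET days, by denominator.**

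- Days 2–56: 24/55 = 44%
- Days 2–56 without the four visit days: 24/51 = 47%
- Days 2–50: 24/49 = 49%
- Days 2–50 without the four visit days: 24/45 = 53%

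Reading any of these as a share of dropouts assumes evenly spread ET visits, an ET MADRS from every dropout, and an ET visit on the day of stopping.

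**Step 4: relax those assumptions.** A simulation used visits varying by ±1 day. Stop days were uniform, early-loaded or late-loaded. A scheduled visit counted as attended only if it came before the stop day.

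| Lag from stopping to ET visit | Uniform | Early-loaded | Late-loaded |
|---|---|---|---|
| None | 44% | 38% | 42% |
| 0–3 days | 33% | 28% | 32% |
| 0–7 days | 21% | 17% | 20% |

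Missed ET visits lower the share of all dropouts further. With no lag and 60–80% attendance, 44–53% becomes 0.6 × 44% = 26% up to 0.8 × 53% = 43%. The logical limits are 0% and 100%.

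**Step 5: effect on the LOCF contrast (illustration only).** Shift = share overridden × worsening between the two scores × difference in dropouts / 50 per arm. Assume 9 versus 3 dropouts and 5 to 8 points of worsening.

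- Share 47%: 0.47 × 5 × 6/50 = 0.28, up to 0.47 × 8 × 6/50 = 0.45 point.
- Share 17–33%: 0.17 × 5 × 6/50 = 0.10, up to 0.33 × 8 × 6/50 = 0.32 point.
- Equal dropout and equal worsening: zero.

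**The case against.** Preferring the scheduled score is a sensible tie-break. The MMRM takes one value per visit, and SAP 6.3 favours the value nearest the nominal day. The score kept is at most about a week older than the one set aside, and a change of 5 to 8 points over that gap in every such patient would be extreme. ET scores remain in the listings. All of this stands, and it is why the window rule need not change for by-visit summaries or the primary MMRM. It does not rescue LOCF, because SAP 6.4 and 15.1.4 carry the tie-break into imputation.

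A reader might infer three stronger points that the documents do not support.

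- **That about half of dropouts are affected.** No dropout timing or ET attendance is given. ET visits are only encouraged (Protocol Table 1, footnote l), and loss to follow-up is a listed reason for leaving. Some stopping triggers are checked at scheduled visits: compliance by visit interval (Protocol 10.8), and the C-SSRS and MADRS item 10 (Protocol 8.3.1). Stopping may therefore cluster on visit days, when there is no later score to lose.
- **That about 6 of 12 dropouts lose their final score.** The step from 44 to 50 per group (1 − 44/50 = 12%) is an allowance in Protocol 13.1 for early leavers who fall out of the analysed population. A patient whose ET score is overridden has a scheduled post-dose MADRS and so is in the Full Analysis Set. The 12% is not a dropout rate for such patients.
- **That the primary MMRM is compromised and ET scores should move to the next visit.** The overridden score is absent from the MMRM and the multiple imputation too, but both keep a recent score from the same window. Reassignment would place a Day 44 score at Week 8, 13 days early and outside the SAP's own window of Day 51 onward. That is a debatable trade-off, not a correction.

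Nor do the documents show that leavers are mostly worsening. The listed reasons also include consent withdrawal, noncompliance, sponsor decision, unblinding and pregnancy.

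**Conclusion.** The point holds for the LOCF sensitivity analysis. The SAP's stated rules set aside an ET MADRS on Days 9–11, 16–22, 30–36 or 44–50 when the scheduled visit in that window was attended on its nominal day. LOCF then carries a score up to 3 days older (Week 1) or 7 days older (Weeks 2, 4 and 6), plus a day for tolerance. This is a written rule that defeats the named method, not merely a missing detail.

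The day count, 24 of 55 (44%, or 44–53% by denominator), follows directly from the SAP table. The share of dropouts does not: 44–53% needs all three assumptions in Step 3, and 17–33% is a reasonable range if ET visits lag by up to 3 or 7 days. The effect on the LOCF contrast is near zero with equal dropout, and about 0.1 to 0.5 point under the assumed unequal dropout and worsening. For scale, the design target is 0.5 SD; with an assumed SD of 8 to 10 that is 4 to 5 points. The sample size and the primary analysis are not in question. The change is worth making because it is cheap and lets the sensitivity analysis do what its name says.

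**What to change.** In SAP 6.4 and 15.1.4, state that LOCF carries the patient's actual last post-baseline MADRS total score from the treatment period, including the ET assessment and excluding the Visit 8 follow-up. Add that the preference for scheduled over ET results does not apply to the LOCF derivation. Visit 8 must be named because MADRS is also collected there, off drug.

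Keep the window rule for by-visit summaries and the primary MMRM. Assigning overridden ET scores to the next visit, in the MMRM or the multiple imputation, should be at most an optional, labelled sensitivity analysis that states how early the values are.

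The cost is about two sentences and a small programming change to one derived dataset. No new data are needed, and the primary result is unchanged.

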## 6.5. STATISTICAL TESTS

Confidence intervals will be reported at the 95% level and all tests will be two-sided, unless otherwise specified in the description of the analyses. P-values will be presented to identify trends in the study. That is, statistical tests that are significant at the 10% level will be considered as demonstrating a trend

Document: C:\Users\q718413\Documents\NEP-MDD-201\_SAP\_v1.0\_Final\_06Dec2018.docx  
 Author: [name]  
 Version Number: 1.0  
 Version Date: 06Dec2018

Template No: CS\_TP\_BS016 Revision 4  
 Effective Date: 01Apr2016  
 Reference: CS\_WI\_BS005

Copyright © 2009, 2010, 2012, 2016 Quintiles Transnational Corp. All rights reserved.  
 The contents of this document are confidential and proprietary to Quintiles Transnational Corp. Unauthorized use, disclosure or reproduction is strictly prohibited.

Analysis Plan

---

and statistical tests that are significant at the 5% level will be considered as demonstrating a strong trend.

## 6.6. COMMON CALCULATIONS

For quantitative measurements, change from baseline will be calculated as:

- Test Value at Visit X – Baseline Value

## 6.7. SOFTWARE VERSION

All analyses will be conducted using SAS version 9.4.

## 7. STATISTICAL CONSIDERATIONS

### 7.1. ADJUSTMENTS FOR COVARIATES AND FACTORS TO BE INCLUDED IN ANALYSES

The following covariates and factors are used in the analyses. For details of their inclusion in the models, see the specific analysis section.

- Baseline score (continuous variable)
- Treatment group (BTRX-246040 or placebo)
- Pooled Investigative Site
- Study visit (Weeks 1 – 8)
- Treatment-by-visit Interaction

If over parameterization means analyses cannot be performed pooling of investigative sites will be considered, if an appropriate pooling is possible, otherwise investigative site will be removed from the analysis.

### 7.2. MULTICENTER STUDIES

This study will be conducted by multiple investigators at multiple centers within the United States. Randomization to treatment arms is not stratified by center.

### 7.3. MISSING DATA

In general, missing data will not be imputed. However, partial dates will contribute to analyses as

---

Document:	C:\Users\q718413\Documents\NEP-MDD-201_SAP_v1.0_Final_06Dec2018.docx		
Author:	[name]	Version Number:	1.0
		Version Date:	06Dec2018

Template No: CS\_TP\_BS016 Revision 4  
Effective Date: 01Apr2016

Reference: CS\_WI\_BS005

Copyright © 2009, 2010, 2012, 2016 Quintiles Transnational Corp. All rights reserved.  
The contents of this document are confidential and proprietary to Quintiles Transnational Corp. Unauthorized use, disclosure or reproduction is strictly prohibited.

Analysis Plan

---

described in [Appendix 2](#). All available data will be included in the safety analysis.

Details for the imputation algorithm for the missing endpoint values for the sensitivity analyses are described in [Section 15.1.4](#) of this analysis plan.

## 7.4. MULTIPLE COMPARISONS/ MULTIPLICITY

The nature of this study is to establish trends and is powered with that intent. Thus, no adjustments will be made for multiple comparisons.

## 7.5. EXAMINATION OF SUBGROUPS

Subgroup analyses will be conducted as stated in the exploratory analysis sections. It should be noted that the study was not designed to detect treatment differences with high statistical power within subgroups.

The following subgroups will be assessed and described within the exploratory analysis sections:

- Gender.
- Baseline severity of anhedonia symptoms (SHAPS) score ( $\leq 4$ ,  $> 4$ ).
- Baseline severity of anhedonia symptoms (SHAPS) score ( $\leq 7$ ,  $> 7$ ).
- Baseline anxiety, as assessed by the Hamilton Anxiety Rating Scale (HAMA-A) score ( $< 20$ ,  $\geq 20$ )

## 8. OUTPUT PRESENTATIONS

[APPENDIX 1](#) shows conventions for presentation of data in outputs.

The shell templates provided with this SAP describe the presentations for this study and therefore the format and content of the summary tables, figures and listings (TFLs) that will be provided by IQVIA Biostatistics.

## 9. DISPOSITION AND WITHDRAWALS

All patients who provide informed consent will be accounted for in this study.

Patient disposition, withdrawals and reasons for withdrawal will be presented for the ENR set by treatment group, investigative site and overall.

The number and percentage of patients completing the treatment period will be provided by treatment group and overall. Reasons for discontinuation from the treatment period will be summarized. The proportion of subjects that discontinue early will be compared between treatment groups using Fisher's exact test. The number of subjects that complete and reasons for failing to complete the follow-up visit will be presented for each treatment group. These analyses will be conducted on all patients enrolled,

---

Document:	C:\Users\q718413\Documents\NEP-MDD-201_SAP_v1.0_Final_06Dec2018.docx		
Author:	[name]	Version Number:	1.0
		Version Date:	06Dec2018

Template No: CS\_TP\_BS016 Revision 4  
Effective Date: 01Apr2016

Reference: CS\_WI\_BS005

Copyright © 2009, 2010, 2012, 2016 Quintiles Transnational Corp. All rights reserved.  
The contents of this document are confidential and proprietary to Quintiles Transnational Corp. Unauthorized use, disclosure or reproduction is strictly prohibited.

Analysis Plan

---

the full Analysis Set and the Safety Analysis Set.

In addition, major protocol deviations which lead to exclusion for the PPAS will be summarized by treatment group and protocol violation category for the FAS. Inclusion in all analysis sets will be summarized by treatment group and overall for the RND set.

Listings will be produced to display the information collected in the eCRF regarding patient disposition. Listings will also be generated to show patient randomization assignment, analysis set assignment and all key protocol violations.

## 10. DEMOGRAPHIC AND OTHER BASELINE CHARACTERISTICS

Demographic data and other baseline characteristics will be presented by treatment group and overall.

The following variables will be summarized:

- Age at screening (years) - calculated relative to date of consent
- Sex
- Race
- Ethnicity
- Childbearing potential (females only)
- Height at Screening (cm)
- Weight as Baseline (kg)
- BMI at Baseline (kg/m^2)
- Alcohol consumption status (occurrence, average number of drinks per week)
- Smoking status (occurrence, average number of packs per week)
- Hand Dominance
- Glasses Usage

Categorical variables like sex and ethnicity will be compared between treatment groups using Fisher's exact test for categorical data and continuous variables like age and height will be compared using an ANOVA model with treatment and investigative site as covariates. This analysis will be performed for the FAS, SAF PPAS, CAS and MNRAS sets. Similar comparisons will be conducted for alcohol consumption and smoking status, but only using the SAF set.

All demographic data collected within the eCRF will be listed.

### 10.1. DERIVATIONS

$$\text{BMI (kg/ m}^2\text{)} = \text{weight (kg)/ height (m)}^2$$

---

Document:	C:\Users\q718413\Documents\NEP-MDD-201_SAP_v1.0_Final_06Dec2018.docx	Version Number:	1.0
Author:	[name]	Version Date:	06Dec2018

Template No: CS\_TP\_BS016 Revision 4  
Effective Date: 01Apr2016

Reference: CS\_WI\_BS005

Copyright © 2009, 2010, 2012, 2016 Quintiles Transnational Corp. All rights reserved.  
The contents of this document are confidential and proprietary to Quintiles Transnational Corp. Unauthorized use, disclosure or reproduction is strictly prohibited.

Analysis Plan

---

